7.4.5 Supportive Care Guidelines

7.4.5.1 Rash management

Patients developing dermatologic adverse events while receiving cetuximab should be monitored for the development of inflammatory or infectious sequelae, and appropriate treatment of these symptoms initiated. Below are suggestions for managing cetuximab induced rash:

Antibiotics: As this protocol depends on grading of rash, prophylactic antibiotics may not be used until 3 weeks of neoadjuvant cetuximab has been received and rash assessed, or cetuximab related folliculitis has been determined. The benefit of routine antibiotics in uncomplicated (uninfected) rash is unclear. Some clinicians have used oral minocycline (Minocin), mupirocin (Bactroban), or topical clindamycin (Cleocin). Rash complicated by cellulitis should be treated with appropriate antibiotics based on clinical judgment or microbial sensitivity analysis.

Antihistamines: As this protocol depends on grading of rash, prophylactic Benadryl or Atarax may only be used as necessary during infusion, but not otherwise, until 3 weeks of neoadjuvant cetuximab has been received and rash assessed, or cetuximab related folliculitis has been determined. Benadryl or Atarax may be helpful to control itching.

Topical Steroids: The benefit of topical steroids is unclear. They will not be used prophylactically.

Retinoids: No data to support use. Use is not advised. They will not be used prophylactically.

Benzoyl peroxide: Should NOT be used--may aggravate rash.

Makeup: Rash can be covered with makeup; this should not make it worse (use a dermatologist-approved cover-up, e.g., Dermablend, or any other type of foundation). Remove makeup with a skin-friendly liquid cleanser, e.g., Neutrogena, Dove, or Ivory Skin Cleansing Liqui-Gel.

Moisturizers: Use emollients to prevent and alleviate the skin dryness, e.g., Neutrogena Norwegian Formula Hand Cream or Vaseline Intensive Care Advanced Healing Lotion.

Sunlight: It is recommended that patients wear sunscreen and hats and limit sun exposure while receiving cetuximab as sunlight can exacerbate any skin reactions that may occur.

Over-the-counter medications: Over-the-counter acne vulgaris medications (e.g., benzoyl peroxide) are not advised. This rash is not like acne vulgaris and these treatments could make it worse.³¹

7.4.6 Adherence/Compliance

Patients will receive weekly cetuximab per their medical oncologist. They should adhere to their oncologist's recommendations (based on the protocol) re administration of cetuximab. Failure to do so may result in removal from the study.

7.5 Study Agent (Cisplatin)

Cisplatin is known to bind to DNA and produces inter-strand cross links. It is thought that the most likely mechanism of antitumor action of this drug resides in its ability to inhibit DNA synthesis and to a lesser degree, RNA and protein synthesis. Each vial contains 10 mg of DDP, 19 mg of sodium chloride, 100 mg of mannitol, and hydrochloric acid for pH adjustment. One vial is reconstituted with 10 ml of sterile water. The pH range will be 3.5 to 4.5. Cisplatin injection also is available from the manufacturer in aqueous solution, each ml containing 1 mg cisplatin and 9 mg NaCl and HCl or NaOH to adjust pH. Reconstituted solution of cisplatin is stable for 20 hours when stored at 27°C and should be protected from light if not used within 6 hours. Refer to package insert for additional information.

7.5.1 Dose Calculation

Doses will be calculated on day 1 of each cycle using the patient's actual weight in the determination of body surface area. A variance of 10% of the calculated total dose will be allowed.

BSA (m²) =

$$\sqrt{\frac{(height) \times (weight)}{3131}}$$

For the determination of body surface area, height is measured in inches and weight is measured in pounds. If a weight change of $\geq 10\%$ occurs, the cisplatin dose should be recalculated.

7.5.2 Treatment Administration

Patients who do not respond to or progress through neoadjuvant cetuximab will receive cisplatin, 100 mg/m², administered intravenously on approximately Days 1, 22 and 43 of radiation therapy. Days of administration may vary up to two days, and may vary longer if necessary due to toxicity. Alternatively, at the treating medical oncologist's discretion, the patient may instead receive weekly cisplatin 40 mg/m². Note that in order to receive the full dose cisplatin 100 mg/m², the original GFR must be > 60 ml/min. To receive the cisplatin 40 mg/m², the original GFR must be > 50 ml/min.

High dose cisplatin is a highly emetogenic regimen with significant incidence of delayed nausea and vomiting. Institutional guidelines for highly emetogenic regimens

should be followed. In the absence of such guidelines:

For acute nausea and vomiting, premedication should include a 5-HT3 antagonist, such as granisetron, ondansetron, or palonosetron, plus a corticosteroid, such as dexamethasone, up to 20 mg *i.v.*. Breakthrough nausea and vomiting should be managed at the discretion of the medical oncologist or radiation oncologist. Delayed nausea and vomiting (greater than 24 hours after chemotherapy administration) may be managed by the addition of aprepitant concurrently or with metoclopramide and dexamethasone.

Patients must receive vigorous hydration and diuresis. A suggested regimen is prehydration with a 1 liter of D5N S over 2-4 hours and mannitol, 12.5 g *i.v.* bolus immediately prior to cisplatin. Then cisplatin, 100 mg/m², in 500 ml NS is administered over 1-2 hours with an additional 1 to 1.5 liters of fluid given post-hydration. Any pre-existing dehydration must be corrected prior to cisplatin administration. Should extravasation occur, the treating physician should follow institutional guidelines for management. Overnight hospitalization for hydration after cisplatin is strongly encouraged if it is allowed by the patient's insurance company. Additional *i.v.* hydration and BUN/creatinine check should be strongly considered later in the week after cisplatin administration, in order to prevent dehydration and severe fluid/electrolyte imbalance.

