5.1 Inclusion Criteria

A patient is eligible for enrollment if all of the following inclusion criteria are met.

5.1.1 Histologically proven squamous cell carcinoma of the oropharynx, hypopharynx or larynx.

- 5.1.2 Stage III/IVa/b SCC by AJCC 7 criteria (advanced, but not metastatic)
- 5.1.3 Patients must give informed consent.
- 5.1.4 Patients must have an ECOG performance status ≤ 2 (Appendix B).
- 5.1.5 Patients must have normal organ and marrow function as defined below:
 - Platelets $\geq 100,000 / \mu\text{L}$
 - ANC $\geq 1,500 / \mu\text{L}$
 - Hemoglobin $> 8 \text{ g/dL}$ (use of transfusion to achieve this is acceptable)
 - Total bilirubin $< 2 \times$ institutional upper limit of normal (ULN)
 - AST(SGOT)/ALT(SGPT) $\leq 3 \times$ institutional ULN
 - Serum creatinine $< 2 \times$ institutional ULN or creatinine clearance $> 50 \text{ mL/min}$ as determined by 24 hour collection or estimated by Cockcroft-Gault formula

$$\text{CCr male} = \frac{[(140 - \text{age}) \times (\text{wt in kg})]}{[(\text{Serum Cr mg/dL}) \times (72)]}$$

$$\text{CCr female} = 0.85 \times (\text{CrCl male})$$

- 5.1.6 Estimated life expectancy of at least 12 weeks.
- 5.1.7 Negative pregnancy test, if applicable

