5.2 Exclusion Criteria

A patient will not be eligible for this study if any of the following exclusion criteria are met.

- 5.2.1 Patients may not have received previous therapy for their head and neck SCC, including chemotherapy, radiation therapy, or surgery beyond biopsy.
- 5.2.2 Second primary malignancy. Exceptions are 1) patient had a second primary malignancy but has been treated and disease free for at least 3 years, 2) in situ carcinoma (e.g. in situ carcinoma of the cervix), 3) non-melanomatous carcinoma of the skin
- 5.2.3 Patients with metastatic disease beyond the neck and supraclavicular region will be excluded
- 5.2.4 Serious concomitant systemic disorders (including active infections) that would compromise the safety of the patient or compromise the patient's ability to complete the study, at the discretion of the investigator. This includes scleroderma.
- 5.2.5 Age < 18 years.
- 5.2.6 History of allergic reactions attributed to compounds of similar chemical or biologic composition to cetuximab or cisplatin or other agents used in the study.
- 5.2.7 Women who are pregnant, due to the teratogenic effects of radiation therapy and chemotherapy on the unborn fetus. Women of childbearing age must agree to undergo a pregnancy test prior to therapy and to use adequate contraception (hormonal or barrier method of birth control; abstinence) prior to study entry, for the duration of study participation and for 6 months after. Should a woman become pregnant or suspect she is pregnant while participating in this study, she should inform her treating physician immediately.

5.2.8 Patients with HIV infection are not automatically excluded, but must meet the following criteria: CD4 count is $> 499/\text{cu mm}$ and their viral load is $< 50 \text{ copies/ml}$. Use of HAART is allowed.

5.2.9 Due to a small incidence of cardiac related complications with cetuximab EBRT, patients who have had either myocardial infarction, coronary artery bypass graft, coronary artery stenting, hospital admission for heart related issues such as congestive heart failure or arrhythmia *within the last 3 months*, will not be allowed on protocol.

5.2.10 Grade 3-4 electrolyte abnormalities (CTCAE, v. 4):

- Serum calcium (ionized or adjusted for albumin) $< 7 \text{ mg/dl (1.75 mmol/L)}$ or $> 12.5 \text{ mg/dl (> 3.1 mmol/L)}$ despite intervention to normalize levels;

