7.2.5 Determining treatment modality

The patients who receive cisplatin RT will be those who

1. progress by CT RECIST 1.1 criteria during neoadjuvant cetuximab, regardless of rash
2. do not develop either a cetuximab related folliculitis or a partial response by CT RECIST 1.1 criteria

The patients who receive cetuximab RT will be those who

1. develop a cetuximab related folliculitis (at any point following the first cetuximab dose and prior to starting EBRT) without CT progression (ie stable or partial response)
2. have at least a partial response by CT RECIST 1.1 criteria

The dependence of treatment modality on CT response and rash is illustrated by the below table:

CT response by RECIST 1.1

| | Progressive disease | Stable disease | Partial response |
|------|------------------------------------|----------------|------------------|
| Rash | (-) cetuximab related folliculitis | Cis RT | Cetux RT |
| | (+) cetuximab related folliculitis | Cis RT | Cetux RT |

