| Nail loss | Asymptomatic separation of the nail bed from the nail plate or nail loss | Symptomatic separation of the nail bed from the nail plate or nail loss; limiting instrumental ADL | - | - |
| Nail ridging | Asymptomatic; clinical or diagnostic observations only; intervention not indicated | - | - | - |

Rash occurring inside the radiation field may be graded according to the following table from CTCAE 4.0:

| | 1 | 2 | 3 | 4 |
|---|------------------------------------|--|--|--|
| Dermatitis associated with radiation | Faint erythema or dry desquamation | Moderate to brisk erythema; patchy moist desquamation, mostly confined to skin folds and creases; moderate edema | Moist desquamation other than skin folds and creases; bleeding induced by minor trauma or abrasion | Life-threatening consequences; skin necrosis or ulceration of full thickness dermis; spontaneous bleeding from involved site; skin graft indicated |

Cetuximab dose should be modified per the following table in case of severe (grade 3 / 4) rash:

| Occurrence of severe (grade 3/4) acneform rash | Cetuximab modification |
|--|---|
| 1 st occurrence | Delay infusion 1 to 2 weeks. If there is improvement, continue cetuximab at at 250 mg/m ² . If there is no improvement, discontinue cetuximab. |
| 2 nd occurrence | Delay infusion 1 to 2 weeks. If there is improvement, continue cetuximab at at 200 mg/m ² . If there is no improvement, discontinue cetuximab. |
| 3 rd occurrence | Delay infusion 1 to 2 weeks. If there is improvement, continue cetuximab at at 150 mg/m ² . If there is no improvement, discontinue cetuximab. |
| 4 th occurrence | Discontinue cetuximab |

7.4.3.3 Dose modifications for other toxicity: due to lack of evidence that cetuximab contributes to these toxicities, cetuximab dose will not be altered for renal failure, fatigue, nausea/vomiting.

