7.5.3.2 Non-Hematologic Toxicity

Renal Adverse Events: Cisplatin should be administered on the scheduled day of treatment using the following guidelines: If creatinine is > 1.2 mg/dl, clearance must be done in order to make dose adjustment. If the calculated nomogram is 50 mL/min or above, a 24-hour urine collection is not needed, but if the nomogram calculation is less than 50 mL/min, a 24-hour urine collection is mandated.

| Creatinine clearance | Cisplatin dose |
|----------------------|---------------------------|
| > 60 mL/min | 100 mg/m ² |
| 40-50 mL/min | 50 mg/m ² |
| < 40 mL/min | Discontinue and notify PI |

Neurotoxicity: If any signs of grade 3 or greater neurotoxicity occur, discontinue cisplatin. The radiation therapy will continue.

Mucositis: Grade 4 will require a 25% dose reduction

Ototoxicity: For new clinical hearing loss not requiring a hearing aid or for tinnitus that interferes with activities of daily living, treat at 50% dose reduction. For hearing loss requiring a hearing aid, discontinue cisplatin. If the physician is unsure about the severity of the hearing loss, an audiogram is encouraged.

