7.5.5 Supportive Care Guidelines

Patients are allowed to receive full supportive care therapies concomitantly during the study. No other chemotherapy, immunotherapy, hormonal cancer therapy, radiation therapy, surgery for cancer, or experimental medications will be permitted while the patients are participating in this study.

Antiemetic agents

Premedication with a 5HT3 antagonist and corticosteroid is encouraged as discussed in Section 7.4.3.1.

Colony stimulating factors (CSFs)

CSFs are not permitted as primary prophylactics. If, in the Investigator's opinion it is required in the presence of severe neutropenia (ANC $<500/\mu\text{l}$ for at least 3 days) with or without the presence of documented infection then use of CSFs must be discontinued at least 24 hours prior to the start of the next cycle of chemotherapy. If a patient develops hematologic toxicities, chemotherapy dose reduction and acute treatment of neutropenia are

recommended, rather than chemotherapy dose maintenance and pre-emptive treatment with CSFs.

Erythropoietin use is not permitted as it has been demonstrated to have a detrimental effect on HNSCC tumor control. Blood transfusions are permitted at the oncologists' discretion.

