- d) General or specific changes in the patient's condition render the patient unacceptable for further treatment in the judgment of the investigator
- e) Protocol violation - any patient found to have entered this study in violation of the protocol might be discontinued from the study at the discretion of the Principal Investigator.

11. Laboratory Evaluations and Procedures/Correlative and Pharmacokinetic Studies

11.1 An overview of the possible molecular investigations, and in order of priority include

1. FoundationOne genomic profile from paraffin embedded tumor samples taken before cetuximab or after locoregional/distant failure
2. RNA sequencing of tumor samples before and after cetuximab
3. RNA sequencing of skin samples before and after cetuximab
4. DNA sequencing of tumor and skin samples before and after cetuximab
5. IHC analysis of EGFR downstream pathways that are illuminated by the above

The laboratory investigations are very comprehensive, ranging from partial DNA sequencing (FoundationOne™ (or other certified genomic analysis facility)) in order to check for a battery of known DNA mutations related to cancer, to RNA sequencing on fresh tissue, which will shed light on how protein production is altered when the tumor is treated with cetuximab. FoundationOne™ (or other certified genomic analysis facility) is targeted DNA sequencing that is performed on paraffin embedded tumor samples. As a pan-cancer test, FoundationOne™ (or other certified genomic analysis facility) is designed to interrogate the entire coding sequence of 236 cancer-related genes (3,769 exons) plus 47 introns from 19 genes often rearranged or altered in cancer. These genes are known to be somatically altered in human solid cancers based on recent scientific and clinical literature.^{32 33} In addition, RNA sequencing will be performed on tumor samples from before and after neoadjuvant cetuximab, to investigate changes in protein production caused by cetuximab ie changes in protein production downstream in the EGFR pathway or completely alternate pathways that may be triggered by cetuximab. In addition, HPV status can be easily determined from RNA sequencing. Once the cDNA library is created by Cancer Institute of New Jersey Functional Genomics ([name]), analysis will be performed by Cancer Institute of New Jersey bioinformatics ([name]).

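### Renal eligibility admits patients with creatinine clearance of 50 mL/min or less, whom the plan then assigns to cisplatin under rules that conflict at 40-50 mL/min and name no treatment below 40

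*Combined protocol and SAP*

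**What the plan says.** Four sections of the combined protocol and SAP bear on this.

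- **Entry (5.1.5).** The renal criterion has two limbs, joined as "institutional ULN or creatinine clearance". Serum creatinine below 2 × ULN is enough alone, and so is clearance above 50 mL/min by 24-hour collection or Cockcroft-Gault. A patient who passes on creatinine need not have clearance calculated.
- **Assignment (7.2.5, 7.5.2).** Cisplatin with radiation goes to patients whose disease progresses on CT and to those who "do not develop either a cetuximab related folliculitis or a partial response by CT RECIST 1.1 criteria". The rule has no renal condition.
- **Cisplatin entry floors (7.5.2).** The 100 mg/m² regimen needs an original GFR above 60 mL/min. For weekly 40 mg/m², "the original GFR must be > 50 ml/min".
- **Renal dosing (7.5.3.2).** A table under renal adverse events gives 50 mg/m² at 40-50 mL/min. Below 40 the instruction is "Discontinue and notify PI".

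Section 7.5.5 closes off substitutes for patients on study: "No other chemotherapy, immunotherapy, hormonal cancer therapy" and several other treatments are not permitted.

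**The concern.** Read in sequence, these rules can enrol a patient, give three weeks of cetuximab, and then assign a systemic treatment that the same plan withholds at that patient's baseline renal function. Section 17.2 itself identifies delay of cisplatin with radiation in patients unresponsive to cetuximab as the possible added danger of the protocol. Finding out only then that cisplatin is barred adds to that risk and leaves the choice of treatment to case-by-case judgment.

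There is also a smaller reporting issue. Two-year locoregional control in non-responders is a secondary outcome (16.4). Substitutes chosen ad hoc would be mixed into it without a rule for identifying or reporting them.

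**Working it through.** The plan gives no figure to reproduce here. The check is whether the creatinine limb really admits clearance of 50 mL/min or less, and what the plan then prescribes.

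**Inputs.** From 5.1.5: CCr = (140 − age) × weight / (72 × Cr), multiplied by 0.85 for women. From 7.5.2 and 7.5.3.2: the floors of 50 and 40 mL/min. From 16.2: 27 patients and a 60% response rate. Assumptions: two illustrative patients (man, 65 years, 70 kg; woman, 70 years, 60 kg); ULN of 1.0 to 1.3 mg/dL, since the documents give none; and original GFR in 7.5.2 taken as the same quantity as creatinine clearance.

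**Step 1: creatinine at which clearance equals each floor.**

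| Patient | Cr at 50 mL/min | Cr at 40 mL/min |
|---|---|---|
| Man | 75 × 70 / (72 × 50) = 5250 / 3600 = 1.46 | 5250 / 2880 = 1.82 |
| Woman | 0.85 × 70 × 60 / 3600 = 3570 / 3600 = 0.99 | 3570 / 2880 = 1.24 |

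**Step 2: compare with the entry limit.** Twice a ULN of 1.0 to 1.3 is 2.0 to 2.6 mg/dL. All four values in step 1 are below even the lower figure, so both patients can qualify on creatinine with clearance below 50, and below 40.

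**Step 3: clearance at the entry limit.** At Cr 2.0 and 2.6, the man has 5250 / 144 = 36.5 and 5250 / 187.2 = 28.0 mL/min. The woman has 3570 / 144 = 24.8 and 3570 / 187.2 = 19.1. These are worst cases, not typical patients.

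**Step 4: what the plan prescribes for a non-responder.**

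| Baseline clearance | 7.5.2 | 7.5.3.2 table | Result |
|---|---|---|---|
| 40-50 mL/min | Both regimens barred | 50 mg/m² | Conflict |
| Below 40 mL/min | Both regimens barred | Stop, tell the PI | No treatment named |

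**Step 5: does a later check catch this?** Only in part. Section 7.5.3.2 requires clearance when creatinine exceeds 1.2 mg/dL. The woman above has 3570 / (72 × 1.1) = 45 mL/min at 1.1 and 3570 / (72 × 1.2) = 41 at 1.2, and triggers nothing there. The 7.5.2 floor does require a baseline GFR, but as a condition for giving cisplatin, not for enrolment.

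**Step 6: how many patients.** Expected non-responders are 27 × 0.40 = 10.8, about 11. The share with clearance of 50 or less cannot be derived from the documents. If it were 5% to 20% (an assumed range), 10.8 × 0.05 = 0.5 to 10.8 × 0.20 = 2.2 patients would be affected.

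**The case against.** The strongest reply is that the plan does not leave all these patients without a rule. A reader might infer that nothing is written for anyone at 50 mL/min or less. That goes too far, because 7.5.3.2 prints a cisplatin dose for 40-50 mL/min and is worded for the scheduled day of treatment. This part of the reply stands: in that band the text is contradictory, not silent. It does not settle the matter. The row sits among dose modifications for renal adverse events, and if applied at baseline it gives 50 mg/m² to a patient for whom 7.5.2 rules out even 40 mg/m².

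A second reply is that 7.5.2 protects the patient by withholding cisplatin, and that there are exits. Section 5.2.4 excludes serious disorders that compromise safety or the "ability to complete the study, at the discretion of the investigator". Section 10 allows removal for intercurrent illness, or for changes that "render the patient unacceptable for further treatment in the judgment of the investigator". The 7.5.5 ban does not bind after removal, and the opening of 5.1.5 asks for normal organ function. All true, but none of the exits carries a renal threshold or names a treatment, and 5.1.5 defines normal function by the very criterion at issue. Section 17.2 also argues that radiation would start about when it would off protocol, on a median of 6 weeks from biopsy in 15 local patients. That softens the delay but does not supply the missing treatment.

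Third, the non-responder result is descriptive and unpowered, and already mixes two cisplatin schedules. This stands, and it limits the statistical weight of the point.

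A reader might also infer a dosing gap above 50 and up to 60 mL/min, since the table shows no such row. The documents do not support building on that: the table may not have survived text extraction intact, and 7.5.2 already offers weekly 40 mg/m² to a patient who starts in that range.

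**Conclusion.** The inconsistency is real and follows from the text: 5.1.5 admits patients with clearance of 50 mL/min or less, and every non-responder among them is assigned a drug whose two regimens 7.5.2 bars. At 40-50 mL/min two sections disagree. Below 40 no replacement is named.

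Probably few patients are affected. The figure of about 11 is the expected number of all non-responders, and it should not be read as the number with low clearance, which is unknown. The illustrative clearances rest on an assumed ULN and hypothetical patients. They show that the gap can be reached at unremarkable creatinine values, not how often it will be.

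The consequences are for patient safety, conduct and the descriptive non-responder locoregional control. A reader might infer a threat to the main result, but the primary endpoint is locoregional control in cetuximab responders, who do not receive cisplatin under 7.2.5, so neither it nor its power is touched. This is a cheap improvement.

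**What to change.** In 5.1.5, require creatinine clearance above 50 mL/min of every patient, calculated at screening, instead of offering it as an alternative to serum creatinine. Each enrolled patient then qualifies on original GFR for at least weekly 40 mg/m². In 7.5.3.2, state that the 40-50 mL/min row applies only to decline on treatment, which removes the conflict with 7.5.2.

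No new procedure is needed, because section 6 already collects creatinine and weight before cetuximab. The target of 27 is unchanged. The cost is that a few patients are excluded, some of whom would have responded and never needed cisplatin; 7.4.3.3 says "cetuximab dose will not be altered for renal failure", so low clearance would not have altered their cetuximab. Accrual slows accordingly. If 5% of candidates were excluded (assumed), 27 / 0.95 = 28.4, so 29 would be needed, and 3 / 0.95 − 3 = 0.16 years, about 2 months, would be added to the planned 3 years. At an assumed 20%, the figures are 27 / 0.80 = 33.75, so 34, and 3 / 0.80 − 3 = 0.75 years, or 9 months.

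If the sponsor prefers to keep these patients, the alternative is to name in 7.5.2 the treatment for a non-responder who cannot have cisplatin, and to report such patients separately.
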